10.2.4.2.3 Disease Control Rate (DCR)

Disease control rate is defined as the percentage of patients who have achieved CR, PR, or SD lasting at least 12 weeks.

10.2.4.2.4 Progression-Free Survival (PFS)

Progression-free survival (PFS) will be calculated as 1+ the number of days from the first dose of study drug to documented radiographic progression, as determined by the Investigator or death due to any cause, whichever occurs first. Patients without a documented event of radiographic progression will be censored on the date of their last adequate tumor assessment (ie, radiologic assessment) or date of first dose of study drug if no tumor assessments have been performed.

For patients who continue treatment post-progression, the first date of progression will be used for the analysis of PFS.

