10.2 Statistical Methods

10.2.1 General Considerations

Data will be summarized using descriptive statistics (number of patients, mean, median, standard deviation, minimum, and maximum) for continuous variables and using frequencies and percentages for discrete variables. Data will be presented by dose cohorts, as appropriate.

Kaplan-Meier methodology will be used to summarize time to event variables.

All data will be used to their maximum possible extent but without any imputations for missing data.

All statistical analyses will be conducted with the Statistical Analysis Software (SAS[®]) system.

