10.2.4 Efficacy Analyses

The efficacy endpoints of ORR, DoR, DCR, and PFS will be evaluated using RECIST v1.1 (Appendix A:) and modified RECIST incorporating irRC (Appendix B). Efficacy endpoints evaluated by the Investigator will be presented for the subgroup of patients determined to be tumor evaluable by the Investigator.

Progression-free survival and OS will also be presented for the safety population.

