10.2.4.2.2 Duration of Response (DOR)

Duration of response for CR and PR will be measured from the date that any of these best responses is first recorded until the first date that PD is objectively documented. For patients who continue treatment post-progression, the first date of progression will be used for the analysis. Patients without a documented event of radiographic progression will be censored on the date of the most recent tumor assessment.

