10.2.4.2.5 Overall Survival

Overall survival (OS) will be calculated as 1+ the number of days from the first dose of study drug to death due to any cause. Patients without a documented date of death will be censored on the date the patient was last known to be alive.

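### The PFS censoring sentence makes no exception for death, so a patient who dies without radiographic progression is both an event and censored

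*Combined protocol and SAP*

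**What the plan says.** Section 10.2.4.2.4 of the combined protocol and SAP measures PFS from first dose to "documented radiographic progression, as determined by the Investigator or death due to any cause, whichever occurs first". The next sentence gives the censoring rule: "Patients without a documented event of radiographic progression will be censored on the date of their last adequate tumor assessment", "or date of first dose of study drug if no tumor assessments have been performed".

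Section 10.2.1 adds only that "Kaplan-Meier methodology will be used to summarize time to event variables". Section 10.2.4 presents efficacy endpoints for the tumor evaluable population and adds: "Progression-free survival and OS will also be presented for the safety population". Section 2.2.2 lists PFS as a secondary endpoint, once under RECIST v1.1 and once under modified RECIST.

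**The concern.** The event definition and the censoring rule do not match. An event is progression or death, but the rule for having no event looks only at progression. A patient who dies without documented radiographic progression meets both sentences, and a programmer could follow either.

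If the censoring sentence is followed, those deaths leave the event count and are censored back at the last scan. Patients who die are not a random sample of those still at risk, so PFS would look longer than the stated definition gives. The study has no control arm and its introduction cites a single-agent median PFS, so an upward artefact could be taken for benefit of the combination.

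Such patients are plausible here:

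- Section 1.3.1 reports 11 on-study deaths in the earlier rociletinib study, 3 of them not attributed to NSCLC progression (pulmonary embolism, pneumonia, unknown cause).
- Section 11.1 stops treatment for clinical progression, and Appendix A recognises symptomatic deterioration without objective progression.
- Section 8.4.3.1 ends scans when all study treatment stops, although Section 11.1 mentions later progression follow-up. Section 8.3 keeps collecting survival, so later deaths will be on record and must be classified.
- Under Appendix B, new lesions alone and non-target lesions do not make progression. Modified-RECIST PFS therefore leaves more room for death without qualifying progression.

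**Working it through.** **Step 1: compare each endpoint's event with its censoring trigger.**

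| Endpoint | Event | Censoring trigger | Match? |
|---|---|---|---|
| DOR (10.2.4.2.2) | Objective progression only | "Patients without a documented event of radiographic progression will be censored on the date of the most recent tumor assessment" | Yes |
| PFS (10.2.4.2.4) | Progression or death, whatever the cause | "Patients without a documented event of radiographic progression will be censored on the date of their last adequate tumor assessment" | No: death is missing |
| OS (10.2.4.2.5) | Death | "Patients without a documented date of death will be censored on the date the patient was last known to be alive" | Yes |

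The PFS trigger has the same wording as the DOR trigger, where it fits because DOR ends only at progression. The word radiographic is explicit, so the phrase cannot be stretched to cover death. No other section restates the PFS rule.

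**Step 2: which population is exposed to censoring at first dose.** Section 10.1 requires a tumor assessment after baseline for the tumor evaluable population. A patient who dies before any such scan is not in it. Only the safety-population PFS can contain that patient, so only there could the literal rule censor a death as early as first dose. Deaths after at least one scan are affected in both populations.

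**Step 3: size.** The plan gives no PFS estimate, event count or power, so there is no figure to reproduce. For illustration only:

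- Reference median: 10.4 months, rociletinib monotherapy after acquired resistance (Synopsis and Section 1).
- f: share of first events that are deaths without radiographic progression. Assumed 5% to 20%; not in the documents.
- Independent exponential times to progression and to death without progression.

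Total hazard is λ = ln 2 / 10.4 = 0.0666 per month. Censoring the deaths leaves (1 − f)λ, so the Kaplan-Meier median becomes 10.4/(1 − f):

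- f = 5%: 10.4/0.95 = 10.9 months
- f = 10%: 10.4/0.90 = 11.6 months
- f = 20%: 10.4/0.80 = 13.0 months

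Simulation on the planned scan schedule (weeks 6, 12 and 18, then every 9 weeks) agrees in direction. Six-month PFS was 75% with deaths counted and 78% under the literal rule at f = 10%, and 74% against 80% at f = 20%. These baselines exceed the smooth exponential value, exp(−0.0666 × 6) = 67%, because six months falls just before the week-27 scan. The two illustrations should not be mixed.

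**Step 4: deaths before the week-6 scan (safety population).** Six weeks is 42/30.4375 = 1.38 months. The expected share of patients is 1 − exp(−λ × f × 1.38): 0.5% at f = 5%, 0.9% at 10% and 1.8% at 20%. In a group of 50 that is under one patient, if the hazard is constant.

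**The case against.** The strongest reply is that this is a drafting slip with an obvious reading. The definition comes first, a patient who has died has had an event under it, and censoring applies to patients without an event. The trigger looks carried over from DOR. That account of intent is probably right, but the text does not state it, and the sentence that would be programmed says something else.

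The limits on consequence also stand. The Phase 2 primary endpoint is ORR (Section 10.2.4.1). The futility rules in Section 10.3 use response only, Section 10.2.4.2.6 plans no comparison between groups or subgroups, and no PFS threshold exists. With 25 and 50 patients, the binomial standard error around 75% is √(0.75 × 0.25/25) = 9 points and √(0.75 × 0.25/50) = 6 points, so the simulated 3 to 6 point shift is no larger than about one standard error in either group.

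Four stronger inferences are tempting and not supported:

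- That the plan means to exclude deaths from PFS. The event definition says the opposite.
- That early deaths are censored at first dose in every PFS analysis. The tumor evaluable population excludes those patients, so this concerns the safety population alone.
- That PFS will be overstated by a known 1 to 3 months. That rests on an assumed f, on independent exponential times, and on the censoring sentence overriding the definition.
- That the trial's comparison with 10.4 months is biased. No such comparison is planned, and the figure is no benchmark for Group A, which is TKI- and chemotherapy-naïve.

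**Conclusion.** The contradiction is real and unresolved in the documents: death without documented radiographic progression is both a PFS event and a reason for censoring. Followed literally, the censoring sentence biases PFS upward. The direction holds for any f above zero in the model used. The amount is unknown because f is unknown, and the 10.9, 11.6 and 13.0 months are illustrations for a Group B-like setting, not predictions. Censoring as early as first dose is confined to the safety-population PFS and would probably involve very few patients.

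PFS is secondary and descriptive and drives no sizing or stopping decision, so this is a should-fix, to be settled before the PFS analysis is programmed.

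**What to change.** Replace the censoring sentence with one whose trigger mirrors the event, for example: *Patients with neither documented radiographic progression nor death are censored at their last adequate tumor assessment or, if no tumor assessment was performed, at the date of first dose.* State that it applies to PFS under RECIST v1.1 and modified RECIST, in both the tumor evaluable and the safety populations. The DOR sentence can stay, because it matches its own definition.

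No new data or design change is needed. PFS may come out slightly shorter than under the literal rule. The statistical text sits in protocol Section 10, so the correction needs a protocol amendment, with the IRB approval that Section 12.7 requires, or a clarification in a separate SAP.

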10.2.4.2.5 Overall Survival

Overall survival (OS) will be calculated as 1+ the number of days from the first dose of study drug to death due to any cause. Patients without a documented date of death will be censored on the date the patient was last known to be alive.

10.2.4.2.6 Exploratory Sub-Group Analyses

For Phase 2 of the study, accrual to Groups A and B will take place independently.

In Group B, T790M+ and T790M– patients will be enrolled concurrently. Exploratory subgroup analyses will be performed.

There are no planned statistical analyses between Group A and B or the sub-groups within Group B.

10.2.4.2.7 PK Analyses

Blood sampling for PK analyses of both rociletinib and MPDL3280A will be conducted in all patients treated with rociletinib and MPDL3280A. PK parameters, including AUC₀₋₂₄, C_{max} , C_{min} , and t_{max} will be estimated for rociletinib, and C_{max} , and C_{min} for MPDL3280A using non-compartmental models. Comparisons across dose levels will be made to assess proportionality.

10.2.4.2.8 Pharmacodynamics Analyses

Tumor tissue, plasma, and blood specimens will be used for pharmacodynamic assessment of rociletinib and/or MPDL3280A activity, to evaluate the concordance of mutant EGFR detection between tissue and plasma, and to explore biomarkers that may be predictive of response or resistance to rociletinib and/or MPDL3280A. Biomarkers and changes in biomarker status will be investigated for associations with rociletinib and/or MPDL3280A exposure, safety, and clinical activity. Given the limited sample size, no formal statistical analysis is planned.

10.2.5 Safety Analyses

The safety analyses will be performed using the safety population.

Safety data analysis will be conducted on all patients receiving at least one dose of rociletinib or MPDL3280A. The number and percentage of patients experiencing one or more AEs will be summarized by dose level group, relationship to study drug, and severity. AEs will be coded using MedDRA terminology. Listings of patients who experienced DLT during Cycle 1, dose reductions, dosing interruptions, withdrawal due to an AE, SAEs and/or death will be presented. Laboratory parameters will be summarized using descriptive statistics, by post-dosing shifts relative to baseline, and data listings of clinically significant abnormalities. Vital signs, ECOG performance status, and ECG data will be summarized by changes from baseline values at each dose level using descriptive statistics.

A mTPI method will be used to identify the MTD or MAD and the RP2D. The mTPI, a model-based approach that has a pre-specified decision matrix that recommends escalating, reducing or maintaining the same dose or stopping dose escalation, based on the toxicities observed in the dose level under evaluation, reduces the risk of exposing patients to doses above the MTD compared with 3+3 design in which there is a 71% chance of escalation if the true but unknown rate of DLT is 20% and less than 50% chance of escalation if the true but unknown rate of DLT is higher than 30%.

10.2.5.1 Extent of Exposure

The following will be summarized by dose group:

- Number of weeks of treatment initiated;
- Number of dose reductions or interruptions.

The number of weeks of treatment initiated will be investigated by summarizing the number of weeks started by each patient for each study drug. The number of patients with at least one dose reduction or interruption will be summarized with frequencies and percentages separately for each study drug and for the combination.

10.2.5.2 Adverse Events

Adverse event (AE) coding will be performed using MedDRA terminology. The severity of the toxicities will be graded according to the NCI CTCAE v4.03 whenever possible. Treatmentemergent AEs are defined as AEs with an onset date on or after the date of first dose of rociletinib or MPDL3280A until the date of the last dose of either study drug plus 28 days. AEs will be considered treatment-emergent if all or part of the date of onset of the AE is missing and it cannot be determined if the AE meets the definition for treatment-emergent.

The number and percentage of patients who experienced treatment-emergent AEs for each system organ class and preferred term will be presented by dose group. Multiple instances of the treatment-emergent AEs in each System Organ Class and multiple occurrences of the same Preferred Term are counted only once per patient. The number and percentage of patients with at least one treatment-emergent AE will also be summarized by dose group.

Separate tables will present the following by dose group and study phase:

- All treatment-emergent AEs;
- Treatment-emergent AEs by CTCAE grade;
- Grade 3 or greater treatment-emergent AEs;
- Grade 3 or greater treatment-related, treatment-emergent AEs;
- Treatment-related, treatment-emergent AEs;
- Dose-limiting toxicity AEs;
- Serious treatment-emergent AEs;

- Serious treatment-related, treatement-emergent AEs;
- Treatment-emergent AEs with an outcome of death;
- Treatment-emergent AEs leading to discontinuation of either study drug;
- Treatment-emergent AEs resulting in interruption or reduction of either study drug.

The incidence of treatment-emergent AEs will be summarized by relationship to oral study drug using "treatment-related" and "not treatment-related" categories. If a patient experiences multiple occurrences of the same AE with different relationship categories, the patient will be counted once as a relationship category of treatment-related.

If a patient experiences multiple occurrences of the same AE with different intensity toxicity grades, the patient will be counted once for the maximum (most severe) toxicity grade. AEs with a missing intensity will be presented in the summary table with a toxicity grade of "Missing." For each toxicity grade, the number and percentage of patients with at least one treatment-emergent AE of the given grade will be summarized.

Non-treatment-emergent AEs (pre-treatment and post-treatment) will be presented in the data listings.

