3.2.1 Dose-Limiting Toxicity

Determination of DLTs will be made during the first 21 days of combination treatment with rociletinib and MPDL3280A (ie, during Cycle 1 after the rociletinib Run-in-Period) in the Dose Finding Phase. A DLT is defined as a clinically significant AE or laboratory abnormality assessed as at least related to the study drug (rociletinib and/or MPDL3280A), unrelated to disease progression, and that meets any of the following criteria:

Cytopenia:

- Grade 4 neutropenia persisting for more than 7 days;
- Febrile neutropenia, defined as an absolute neutrophil count (ANC) < 1000/mm³ and a single temperature of > 38.3°C (101°F);
- Grade 4 thrombocytopenia persisting for more than 7 days or thrombocytopenia with clinically significant bleeding (ie, bleeding that requires blood or platelet transfusion or other medical intervention, or that may cause disability or death, such as cerebral hemorrhage).

Organ Toxicity:

• Grade \geq 3 symptomatic hepatic toxicities lasting for > 48 hours, or Grade \geq 3 asymptomatic hepatic toxicities lasting for > 7 days with the following exception:

- For patients with Grade 2 Alkaline phosphatase (ALP) abnormality at baseline, an increase to > 8 × the upper limit of normal (ULN) lasting > 48 hours (if symptomatic) or > 7 days (if asymptomatic) will be considered a DLT.
- Grade \geq 3 nonhematologic, nonhepatic organ toxicity, with the following exceptions:
 - **DLT Toxicity Exceptions**
 - Grade 3 nausea, vomiting, or diarrhea that resolves to Grade ≤ 1 within 7 days after starting appropriate supportive therapy (see Section 6.2.2);
 - Grade ≥ 3 asymptomatic or mildly symptomatic rash that can be adequately managed with supportive care (see Section 6.2.4) or symptomatic rash that resolves to become asymptomatic and/or Grade ≤ 2 within 7 days of appropriate supportive therapy;
 - Grade \geq 3 fatigue that resolves to Grade \leq 2 within 7 days;
 - Grade 3 arthralgia that can be adequately managed with supportive care or that resolves to Grade ≤ 2 within 7 days;
 - Grade 3 autoimmune thyroiditis or other endocrine abnormality that can be managed by endocrine therapy and that would not necessitate initiation of systemic corticosteroids;
 - Grade 3 fever (in the absence of any clinically significant source of fever) that resolves to Grade ≤ 2 within 7 days with supportive care;
 - Grade 3 laboratory abnormality that is asymptomatic and deemed by the Investigator to be not clinically significant;

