5.4 Blinding/Masking of Treatment

This is an open-label study; the investigational product will not be blinded or masked. All patients enrolled will receive PO rociletinib and IV MPDL3280A.

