Dose holds for toxicity or for reasons unrelated to toxicity (eg, elective surgery or intercurrent illness) are allowed for up to 14 days for rociletinib and for up to 42 days (2 cycles) for MPDL3280A. Permission for a longer dose hold must be granted by the Sponsor's Medical Monitor; in the absence of such permission, the patient should permanently discontinue all study treatment (Section 11.1).

Intra-Subject Dose Escalation: For patients in the Dose Finding Phase (Phase 1) who have completed 2 cycles of therapy at their original assigned dose with no DLTs, intra-subject dose escalation to a higher dose level of rociletinib (if applicable) may be permitted with approval from the Sponsor's Medical Monitor after consideration of cumulative safety data and provided that the dose level to which the patient will escalate has already been evaluated and has a DLT rate < 33%. Intra-subject dose escalation will begin at the start of a dosing cycle at the Investigator's discretion and requires prior approval by the Sponsor's Medical Monitor. For patients in the Dose Expansion Phase (Phase 2), no intra-subject dose escalation is allowed.

In cases where a patient must discontinue rociletinib or MPDL3280A for toxicity, monotherapy with the other agent may be continued until the patient meets any of the criteria for permanent treatment discontinuation (see Section 11).

A summary of dose modification allowances is shown in Table 8.

	Dose Finding Phase (Phase 1)			Phase 1 and Phase 2		
	Run-In	Cycle 1		Cycle 2+		
	Rociletinib	Rociletinib	MPDL3280A	Rociletinib	MPDL3280A	
Dose Reduction ^a	Not allowed unless due to DLT ^b	Not allowed unless due to DLT or CSC decision	Not allowed	Allowed for toxicity (see Table 7 for dose reductions)	Not allowed	
Dose Hold	Allowed up to 48 hours for toxicity management ^b	Allowed for toxicity; must receive >75% doses to be evaluable for DLT	Not allowed	Allowed up to 14 days ^c for toxicity or reasons unrelated to toxicity	Allowed up to 42 days ^c for toxicity or reasons unrelated to toxicity	

Table 8: Phase 1 and Phase 2 Dose Modification

CSC, Clinical Safety Committee; DLT, dose-limiting toxicity.

^a Dose reductions are permanent.

^b If dose reduction or more than 48-hour delay of rociletinib dosing is required in Run-in-Period, patient will not be eligible for combination therapy but rather will continue rociletinib monotherapy.

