9.6 Adverse Events of Special Interest for MPDL3280A

The conditions listed below are of special interest and should be recorded within 24-48 hours of their occurrence.

Conditions suggestive of an autoimmune disorder:

- Pneumonitis;
- Hypoxia or Dyspnea \geq Grade 3;
- Colitis;
- Endocrinopathies: diabetes mellitus, pancreatitis, or adrenal insufficiency;
- Vasculitis;
- Hepatitis;
- Transaminitis: AST or ALT > 3 × ULN and bilirubin > 2 × ULN or AST/ALT > 10 × ULN;
- Systemic lupus erythematosus;
- Guillain barre syndrome;
- Myasthenia gravis;
- Pericardial effusion;
- Skin Reactions: vitiligo or pemphigoid;
- Events suggestive of hypersensitivity, cytokine release, influenza-like illness, SIRS, or infusion reaction syndromes.

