9.7 Recording of AEs and SAEs

Any AE from the time the first dose of either study drug through 28 days after the last dose of study drug will be recorded on the AE eCRF. Study procedure-related AEs that occur after signing of the ICF and before first dose of either study drug will also be captured on the AE eCRF. Any other AE that occurs before first dose of study drug should be recorded on the Medical History eCRF. In order to avoid vague, ambiguous, or colloquial expressions, the AE should be recorded in standard medical terminology rather than the patient's own words. Whenever possible, the Investigator should combine signs and symptoms that constitute a single disease entity or syndrome. For example, fever, headache, and nasal discharge may be reported as coryza, if that is a reasonable diagnosis. The existence of an AE may be concluded from a

spontaneous report of the patient; from the physical examination; or from special tests such as the ECG, laboratory assessments, or other study-specified procedure.

Each AE is to be evaluated for duration, severity, seriousness, and causal relationship to each study drug. The action taken and the outcome must also be recorded.

SAEs that occur during the study or within 28 days after receiving the last dose of either study drug, whether or not related to rociletinib or MPDL3280A, must be immediately reported to the Sponsor/designee SAE contact (Section 9.9).

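### Section 10.2.5.2 judges AE relatedness against the oral drug only, so an event attributed solely to IV MPDL3280A would be tabulated as not treatment-related

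*Combined protocol and SAP*

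**What the plan says.** Section 10.2.5.2 lists 11 treatment-emergent AE tables. A separate sentence then gives the rule for relatedness: "The incidence of treatment-emergent AEs will be summarized by relationship to oral study drug", with two categories, treatment-related and not treatment-related. A patient with several occurrences of the same AE in different categories is counted once, as treatment-related.

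Section 5.4 identifies the two drugs and their routes: "All patients enrolled will receive PO rociletinib and IV MPDL3280A".

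Other sections treat relatedness, or the drugs generally, without restriction to the oral one:

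- Section 10.2.5, the parent section: "The number and percentage of patients experiencing one or more AEs will be summarized by dose level group, relationship to study drug, and severity".
- Section 9.7, on recording: "Each AE is to be evaluated for duration, severity, seriousness, and causal relationship to each study drug".
- Section 3.2.1 counts a toxicity as dose-limiting if it is related to rociletinib, MPDL3280A or both.
- Section 10.2.5.1 reports dose reductions and interruptions "separately for each study drug and for the combination".
- Within Section 10.2.5.2 itself, the treatment-emergent window and the discontinuation and interruption tables refer to either drug.

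**The concern.** The study exists to characterise a combination. A relatedness rule tied to one partner puts toxicity caused by the other partner in the column that readers take to mean not caused by treatment.

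Events attributable to MPDL3280A alone are foreseen. Section 9.6 lists its events of special interest, including "Events suggestive of hypersensitivity, cytokine release, influenza-like illness, SIRS, or infusion reaction syndromes". Section 5.7.4 distinguishes toxicity related to rociletinib from toxicity related to MPDL3280A. It also says: "In cases where a patient must discontinue rociletinib or MPDL3280A for toxicity, monotherapy with the other agent may be continued". A patient can therefore be on MPDL3280A alone while still inside the treatment-emergent window, which runs to 28 days after the last dose of either drug.

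At stake are an understated share of patients with treatment-related toxicity and possible disagreement between tables in the same report.

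**Working it through.** The plan states no figure for this point, so there is none to reproduce. The check has three parts.

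**1. Apply the rule as written to each attribution.**

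| Investigator's attribution | Section 10.2.5.2 (oral drug) | Related to either drug (as in the Section 3.2.1 DLT definition) |
|---|---|---|
| Rociletinib only | Related | Related |
| Both drugs | Related | Related |
| MPDL3280A only | **Not related** | **Related** |
| Neither | Not related | Not related |

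Only the third row differs. The rule for repeated occurrences does not repair it: if every occurrence is attributed to MPDL3280A alone, none ever enters the related category.

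**2. Count the tables that could be affected.** Of the 11 listed in Section 10.2.5.2, three carry a treatment-related label: all related events, related events of Grade 3 or greater, and serious related events. The other 11 − 3 = 8 do not use it. The relatedness sentence does not say that it governs those three tables, but it is the only place in Section 10 that ties the label to a drug. If it does govern them, a Grade 3 or greater DLT attributed to MPDL3280A alone would appear in the DLT table and be missing from the Grade 3 or greater related table.

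**3. Size per patient.** If a patient's only related events in a table are attributed to MPDL3280A alone, the reported percentage falls by 100/N points.

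| Group | N | 100/N (points) |
|---|---|---|
| Phase 1 dose group, first 3 evaluable patients (Section 3.2.2) | 3 | 33.3 |
| Phase 1 dose group of 6 (Section 3.2.2 minimum before enrolment can stop) | 6 | 16.7 |
| Phase 1 dose group, 3 + 6 if the dose is maintained | 9 | 11.1 |
| All Phase 1 | 18 | 5.6 |
| Group A, if shown separately | 25 | 4.0 |
| Group B, if shown separately | 50 | 2.0 |
| All Phase 2 | 75 | 1.3 |

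These are weights per patient, not predictions. The total understatement is the number of such patients times the weight, and the documents give no rate for MPDL3280A-only attribution. Planned numbers are used. Phase 1 patients who stay on rociletinib monotherapy after the run-in are replaced but still belong to the safety population, so actual denominators may be somewhat larger.

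**The case against.** The strongest reply is that this is a one-word slip. The parent section has no restriction, the rest of Section 10.2.5.2 speaks of either drug, and Appendix H still carries another study's number in a heading, so text carried over from elsewhere is plausible, though unproven. That may explain the wording. It does not change what a programmer working from the more specific rule would produce.

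A second point is that Section 8.4.2.1 refers to Section 9 for the definition of drug-related events, and Section 9.7.2 gives causality categories that name no single drug. These govern how the investigator records causality; they do not define the table label. The point does stand to this extent: only the relationship summary is affected by the text itself, and extending the rule to the three related tables is an inference.

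Third, the effect on the overall percentage may be small. Table 4 reports that 16 of 18 patients (88.9%) on 500 mg BID rociletinib HBr, this study's starting dose, had at least one treatment-related AE on rociletinib alone. If that rate carried over, at most 100 − 88.9 = 11.1% of patients could drop out of the any-related-event row (exact 95% interval for 2 of 18: about 1% to 35%). This is a fair cap for that row, under that assumption. It does not bound the rows for individual terms or the Grade 3 or greater table. For serious events it is almost no limit: Table 3 shows 4 of 18 (22.2%) at that dose, leaving 100 − 22.2 = 77.8%.

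Finally, the safety tables are descriptive and per-drug causality is collected, so correct tables remain possible. That is true, and it limits the harm to labelling.

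**Conclusion.** The concern holds. As written, Section 10.2.5.2 classes any event attributed only to MPDL3280A as not treatment-related, contrary to Sections 3.2.1, 9.7 and 10.2.5. One summary is affected with certainty, and up to three of the 11 listed tables if they use the same rule. The direction is known: related toxicity is understated. The amount is not, because it depends on how many patients have only MPDL3280A-attributed related events.

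The consequence is mislabelling, not loss of data. The eight other tables, the mTPI dose decisions and the Phase 1 primary safety endpoints (treatment-emergent AEs and DLTs) are not directly affected. It should be corrected before the tables are programmed.

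**What to change.** - In Section 10.2.5.2, replace the reference to the oral drug with: relationship to rociletinib, to MPDL3280A, and to either drug.
- State that treatment-related, in every Section 10.2.5.2 table, means related to rociletinib and/or MPDL3280A.
- For repeated occurrences, count the patient as related if any occurrence is related to either drug.
- In Section 10.2.5, add rociletinib and/or MPDL3280A in parentheses after the mention of study drug.
- It would also help to say that the Possibly Related category of Section 9.7.2 maps to treatment-related.

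The either-drug definition alone removes the contradiction. The per-drug columns go further, but they suit a combination study and match how Section 10.2.5.1 already reports dose changes.

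The cost is a few wording edits and some extra table columns. No new data are needed, because causality is already assessed for each drug, and no dose or clinical rule is touched.
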